9.7.1.6 Efficacy Analyses

Where Sleep Diary endpoints are described, the time points refer to the mean of the final 7 nights before the visit unless otherwise stated.

Subjects who discontinue the treatment prematurely will be encouraged to continue to complete the assessments at the protocol defined times (retrieved drop out) until the scheduled time of termination. When available, these data will be used for efficacy analyses. If there are a substantial proportion of early withdrawals, a sensitivity analysis of the primary endpoint will be conducted.

Definitions of Baseline

For the analyses of PBO-controlled endpoints (ie, Day 1 to Month 6), “Study Baseline” is defined as the data captured during the Run-In Period (or during the Baseline Period). For the analyses of data that are not placebo-controlled (ie, Month 7 to Month 12), data from Month 6 visit will be used as the “Period 2 Baseline”. (revised per Amendment 06)

For other endpoints, baseline data are captured during the Run-In and Baseline Period. Details will be specified in the SAP.

12-Month Lemborexant Exposure

Twelve-month (12-month) lemborexant exposure summaries will be summarized by treatment (LEM5, LEM10) and duration of exposure (1 month [30 days] where appropriate, 3 months [90 days], 6 months [180 days], 9 months [270 days] and 12 months [365 days]). Treatment groups are LEM5 and LEM10, and include both (a) LEM Period 1 subjects on the

On-Treatment Full Analysis Set using the change from Study Baseline and (b) LEM Period 2 subjects previously receiving PBO on the On-Treatment Full Analysis Set using the change from Period 2 Baseline. (revised per Amendment 06)

Control of Type 1 Error

A sequential gate-keeping procedure including sSOL (primary endpoint), sSE and sWASO (key secondary endpoints) at Month 6 will control for type 1 error. In order to move from 1 step to the next (steps a to f; below) the outcome must be significant at 0.05 (2-sided).

- a. Change from Study Baseline at Month 6 in sSOL, LEM10 compared to PBO
- b. Change from Study Baseline at Month 6 in sSOL, LEM5 compared to PBO
- c. Change from Study Baseline at Month 6 in sSE, LEM10 compared to PBO
- d. Change from Study Baseline at Month 6 in sSE, LEM5 compared to PBO
- e. Change from Study Baseline at Month 6 in sWASO, LEM10 compared to PBO
- f. Change from Study Baseline at Month 6 in sWASO, LEM5 compared to PBO

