Analyses for persistence versus loss of effect will be conducted for sSOL, sSE, sWASO and sTST at Months 3, 6, 9, and 12 compared to Month 1. Loss of effect will be defined as present if the mean change from Study Baseline at Month 3 (or Months 6, 9, 12) is below the lower bound of the 95% CI at Month 1 for sSE or sTST and above the upper bound of the 95% CI at Month 1 for sSOL and sWASO. Analyses for persistence versus loss of effect over Period 2 will be conducted for only the subjects randomized to PBO in Period 1 (those subjects will have been randomized to lemborexant in Period 2). These analyses will compare sSOL, sSE, sWASO and sTST at Months 9 and 12 to these measures at Month 7. Loss of effect will be defined as present if the mean change from Period 2 Baseline at Month 9 (or Month 12) is below the lower bound of the 95% CI at Month 7 for sSE or sTST and above the upper bound of the 95% CI at Month 7 for sSOL and sWASO. Analyses for persistence versus loss of effect over duration of exposure will be conducted for On-Treatment Full Analysis Set subjects. These analyses will compare 1 month duration of exposure on sSOL, sSE, sWASO and sTST at 3 and 6 months duration of exposure, for (a) LEM Period 1 subjects using the change from Study Baseline and (b) LEM Period 2 subjects

previously receiving PBO using the change from Period 2 Baseline, with loss of effect as defined above. (revised per Amendment 06)

No multiplicity adjustment is planned for other secondary endpoints. (revised per Amendment 03)

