1.1.2 Secondary Objectives

Key Secondary Objectives

- Determine the efficacy of LEM5 and LEM10 compared to PBO on subjective sleep efficiency (sSE) after 6 months of treatment in subjects with insomnia disorder
- Determine the efficacy of LEM5 and LEM10 compared to PBO on subjective wake after sleep onset (sWASO) after 6 months of treatment in subjects with insomnia disorder

Additional Secondary Objectives

- Determine the efficacy of LEM5 and LEM10 compared to PBO on sSOL, sSE, sWASO, and subjective total sleep time (sTST):
 - over the 1st 7 nights of treatment
 - after 1 month of treatment
 - after 3 months of treatment
- Determine the efficacy of LEM5 and LEM10 compared to PBO on sTST at 6 months

- Evaluate the proportions of sleep onset and sleep maintenance responders to LEM5 and LEM10 compared to PBO as defined by response on sSOL or sWASO at 6 months and 12 months
- Evaluate the safety and tolerability of LEM5 and LEM10
- Evaluate the efficacy of LEM5 and LEM10 compared to PBO as measured by responses on the Insomnia Severity Index (ISI) and the Fatigue Severity Scale (FSS) after 6 months
- Evaluate rebound insomnia following discontinuation of treatment
- Evaluate morning sleepiness during and following completion of treatment
- Evaluate persistence of efficacy of LEM5 and LEM10 over 12 months

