3.1.2 Secondary Endpoints

The key secondary endpoints are:

- Mean change from Study Baseline in sSE at Month 6

- Mean change from Study Baseline of sWASO at Month 6

Additional secondary endpoints are:

- Mean change from Study Baseline of sSOL, of sSE, of sWASO and of sTST, at the beginning of treatment (mean of the 7 nights after the 1st dose in Period 1), at Month 1 and at Month 3
- Mean change from Study Baseline of sTST at Month 6
- Proportion of responders at Month 6 and Month 12, where sleep onset responder is defined as follows: sSOL at Study Baseline is ≥ 30 minutes and mean sSOL at 6 months is ≤ 20 minutes, and sleep maintenance responder is defined as follows: sWASO at Study Baseline is ≥ 60 minutes and mean sWASO at 6 months is ≤ 60 minutes and shows a reduction of >10 minutes compared to Study Baseline.
- Change from Study Baseline in daytime functioning, assessed as the total score from the 4 items on daytime functioning, on the ISI, at Months 1, 3, and 6
- Change from Study Baseline on the FSS at Months 1, 3, and 6
- Ratings on the morning sleepiness item of the Sleep Diary, for:
 - The mean change from Study Baseline of the 1st 7 mornings after the 1st dose in Period 1 and Period 2
 - The mean change from Study Baseline at: Month 1, Month 3, and Month 6
 - The mean change from Study Baseline and from Treatment Period 2 Baseline (as appropriate): for subjects with 1, 3, 6, 9 and 12 months exposure
 - The mean change from Screening for the 1st 7 mornings and 2nd 7 mornings of the Follow-up Period
- Rebound insomnia endpoints as assessed from the Sleep Diary during the Follow-up Period
 - Change from Screening of sSOL on each of the 1st 3 nights, mean sSOL of the 1st 7 nights, and mean sSOL of the 2nd 7 nights of the Follow-up Period
 - Change from Screening of sWASO on each of the 1st 3 nights, mean sWASO of the 1st 7 nights and mean sWASO of the 2nd 7 nights of the Follow-up Period
 - Proportion of subjects whose sSOL is longer than at Screening for each of the 1st 3 nights, or whose mean sSOL is longer than at Screening for 1st 7 nights or 2nd 7 nights of the Follow-up Period
 - Proportion of subjects whose sWASO is higher than at Screening for each of the 1st 3 nights, or whose mean sWASO is higher than at Study Baseline for the 1st 7 nights or 2nd 7 nights of the Follow-up Period
- Persistence of Effect
 - Mean change from Study Baseline of sSOL, of sSE, of sWASO and of sTST at Months 3, 6, 9, and 12 compared to Month 1

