The actual value of sSOL and sWASO will be analyzed separately using analysis of covariance model (ANCOVA) with factors of age group (<65 , and ≥ 65 years older), region (North America, Europe and New Zealand, Asia), and treatment for each time point (baseline, each of the first 3 nights, mean of the first 3 nights, mean of the first 7 nights, and mean of the last 7 nights of the Follow-up Period). The 95% CI of the treatment difference will be constructed for each time point. It will be considered as strong evidence of rebound insomnia if the lower bound of the 95% CI of sSOL or sWASO for each of the 3 nights, the mean of the first 3 nights, mean of the first 7 nights, and mean of the second 7 nights of the Follow-up Period exceeds the upper bound of a 95% CI for the values during the Screening Period in the given treatment group. If the LS means for sSOL and sWASO for the Follow-up Period are all lower than for the Screening Period, then no rebound insomnia is suggested. In this analysis, the treatment groups will be defined as the last randomized study treatment just before the Follow-up period.

- Analyses for persistence versus loss of effect will be conducted for sSOL, sSE, sWASO and sTST at Months 2 through Month 12 compared to Month 1.

The 95% CI for the change from Study Baseline of sSOL, sSE, sWASO and sTST at each visit will be calculated using the MMRM model assuming MAR (no missing value imputation) with factors of age group (<65, and ≥65 years older), region (North America, Europe and New Zealand, Asia), treatment, visit and treatment-by-visit interaction as fixed effect, and baseline value as covariate based on FAS. At each month beyond Month 1, the change from Study Baseline will be compared to either the lower bound of the 95% CI (for sSE and sTST) or the upper bound of the 95% CI (for sSOL and sWASO) at Month 1. Persistence of effect will be defined as present if the mean change from Study Baseline at Month 6 is above the lower bound of the 95% CI at Month 1 for sSE or sTST and below the upper bound of the 95% CI at Month 1 for sSOL and sWASO.

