The same analyses for persistence versus loss of effect over Period 2 will compare sSOL, sSE, sWASO, and sTST at Months 7 through 12 to these measures at Month 7 for only the subjects who were randomized to PBO in Period 1 and who continued into Period 2. At each month beyond Month 7, the change from Treatment Period 2 Baseline will be compared to either the lower bound of the 95% CI (for sSE and sTST) or the upper bound of the 95% CI (for sSOL and sWASO) at Month 7. Persistence of effect will be defined as present if the mean change from Treatment Period 2 Baseline at Month 12 is above the lower bound of the 95% CI at Month 7 for sSE or sTST and below the upper bound of the 95% CI at Month 7 for sSOL and sWASO.

Analyses for persistence versus loss of effect over duration of exposure will be conducted for On-Treatment Full Analysis Set subjects. These analyses will compare 1 month of duration of exposure of sSOL, sSE, sWASO and sTST at 3 and 6 months duration of exposure, for a) LEM Period 1 subjects using the change from Study Baseline and (b) LEM Period 2 subjects previously receiving PBO using the change from Period 2 Baseline. At 3 and 6 months duration of exposure, the change from Study Baseline/Treatment Period 2 Baseline will be compared to either the lower bound of the 95% CI (for sSE and sTST) or the upper bound of the 95% CI (for sSOL and sWASO) at 1 month duration of exposure. Persistence of effect will be defined as present if the mean change from Study Baseline/Treatment Period 2 Baseline at 6 months of exposure is above the lower bound of the 95% CI at 1 month of exposure for sSE or sTST and below the upper bound of the 95% CI at 1 month of exposure for sSOL and sWASO.

INSOMNIA SEVERITY INDEX AND FATIGUE SEVERITY SCALE

The following endpoints will be analyzed for the ISI and FSS:

- Change from Study Baseline of the total score from items 1-7, and items 4-7, separately, on the ISI at Months 1, 3, 6 of LEM5 and LEM10 compared to PBO.

- Change from Study Baseline and Treatment Period 2 Baseline (as appropriate) of the total score from items 1-7, and items 4-7, separately, on the ISI for subjects with 3, 6, 9 and 12 months of exposure.
- Change from Study Baseline on the FSS score at Months 1, 3, 6 of LEM5 and LEM10 compared to PBO
- Change from Study Baseline and Treatment Period 2 Baseline (as appropriate) on the FSS score for subjects with 3, 6, 9 and 12 months of exposure.

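### For the arms on lemborexant from Day 1, the SAP decides persistence at Month 6, although the objective is 12 months and the protocol's loss-of-effect rule runs to Month 12

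*SAP*

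**What the plan says.** The secondary objective in SAP 1.1.2 is "Evaluate persistence of efficacy of LEM5 and LEM10 over 12 months". The matching endpoint in SAP 3.1.2 is the change from Study Baseline in sSOL, sSE, sWASO and sTST "at Months 3, 6, 9, and 12 compared to Month 1".

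SAP 3.4.2.4 then sets three persistence rules.

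- **Whole study, FAS.** The analysis runs "at Months 2 through Month 12 compared to Month 1". The month-by-month step is explicit: "At each month beyond Month 1, the change from Study Baseline will be compared to either the lower bound" of the Month 1 interval (sSE, sTST) or the upper bound (sSOL, sWASO). The verdict uses one month only: "Persistence of effect will be defined as present if the mean change from Study Baseline at Month 6 is above the lower bound" for sSE or sTST, and below the upper bound for sSOL and sWASO.
- **Period 2.** Months 7 to 12 are set against Month 7, "for only the subjects who were randomized to PBO in Period 1 and who continued into Period 2". The verdict is read at Month 12.
- **Duration of exposure.** Three and 6 months of exposure are set against 1 month. The verdict is read at 6 months.

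Protocol 9.7.1.6.2 words the first rule as loss rather than persistence: "Loss of effect will be defined as present if the mean change from Study Baseline at Month 3 (or Months 6, 9, 12") falls on the wrong side of the Month 1 limit. The SAP does not carry over a definition of loss of effect.

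**The concern.** Only subjects randomised to lemborexant on Day 1 can reach 12 months of drug; they stay on the same dose through Period 2. They are the only source of evidence on persistence beyond about 6 months, and the verdict for them ignores the second half of their treatment.

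The Period 2 and exposure rules each read their verdict at the last time point of their own comparison. The whole-study rule stops halfway through its own range. Its verdict could be computed at the first of the three database locks in SAP section 3, which holds data only up to Month 6.

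At stake is one stated secondary objective. The report could state that persistence is present under the heading of a 12-month objective, while the protocol's rule, applied to the same means, reports loss of effect at Month 9 or 12.

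**Working it through.** **Plan's own figure.** The documents give no operating figure for the persistence rule. The planning inputs do reproduce: for sWASO, a difference of 11.4 min, SD 43 and 90% power at two-sided 0.05 gives 299 per group, against 300 stated.

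**Step 1: months on lemborexant when each SAP verdict is read.**

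| SAP verdict | Population | Read at | Months on lemborexant |
|---|---|---|---|
| Whole study | Day-1 lemborexant arms | Month 6 | 6 |
| Period 2 | former placebo | Month 12 | 12 − 6 = 6 |
| Exposure | both | 6 months of exposure | 6 |

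No verdict uses months 7 to 12 of drug.

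**Step 2: how far a late loss would pass the limit.** Inputs from the sample-size sections (SAP section 2, protocol 9.7.2): SD of change 43 min (sWASO) and 12 points (sSE), 300 per arm, and the Study 201 LEM5 differences of 11.3 min and 5.5 points. Suppose the arm mean is the same at Months 1 and 6, and the whole of that difference is lost by Month 12.

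Month 1 half-width h = 1.96 × SD/√300:
- sWASO: 1.96 × 43/√300 = 4.87 min
- sSE: 1.96 × 12/√300 = 1.36 points

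Distance beyond the limit = loss − h, since the limit already lies one half-width from the Month 1 mean:
- sWASO: 11.3 − 4.87 = 6.43 min, which is 6.43/4.87 = 1.3 half-widths
- sSE: 5.5 − 1.36 = 4.14 points, which is 4.14/1.36 = 3.0 half-widths

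The SAP verdict, read at Month 6, does not move.

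**Step 3: how often the two readings would disagree (illustration, sWASO).** The difference between a later mean with n subjects and the Month 1 mean has SD s = 43 × √(1/n + 1/300 − 2ρ/300). The within-subject correlation ρ is not in the documents; 0.3 to 0.7 is assumed. The chance of staying inside the limit is Φ((4.87 − loss)/s), with loss 0 at Month 6 and 11.3 at Month 12.

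| Subjects at Month 6 / Month 12 | Persistent at Month 6 | Same rule at Month 12 |
|---|---|---|
| 300 / 300 | 95% to 99% | under 0.1% to 1.4% |
| 150 / 120 (the plan's worst-case retention) | 90% to 94% | 3.7% to 6.4% |

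sSOL is left out because the SAP analyses it on the log scale and gives no SD on that scale.

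**The case against.** The strongest reply is that nothing is hidden. The SAP compares every month up to Month 12 with the Month 1 limit, keeps the Months 3, 6, 9 and 12 endpoint, summarises the diary measures at 9 and 12 months of exposure, and reports responders monthly for Months 7 to 12. A late fade would be plain in the tables. This stands: the gap is in one predefined verdict, not a missing analysis.

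Three stronger readings are tempting, and the documents do not support them.

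- A reader might infer that no persistence verdict can be affected by Months 7 to 12. The Period 2 verdict is read at calendar Month 12, and for former-placebo subjects the exposure verdict also falls in Period 2. Only the Day-1-arm verdict is insensitive to those months.
- A reader might infer that all three SAP rules depart from the protocol. Protocol 9.7.1.6.2 itself limits the Period 2 analysis to former-placebo subjects and the exposure analysis to 3 and 6 months. Only the first rule differs.
- A reader might infer that the change went unrecorded. SAP section 5 does not list it but refers to Table 1, which logs added clarity on persistence. That entry does not mention Month 6, and the documents do not show when the Month 6 rule entered.

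The stakes are also limited: there is no multiplicity control here, no hypothesis test after Month 6 and no placebo group in Period 2.

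**Conclusion.** The point holds for the Day-1 lemborexant arms. Their SAP verdict rests on the Month 6 mean alone, while the objective, the SAP's own endpoint and the protocol's rule all extend to Month 12. The same data can therefore yield persistence under one document and loss of effect under the other.

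In the illustration, the late loss exceeds the Month 1 limit by 1.3 half-widths for sWASO and 3.0 for sSE and leaves the SAP verdict unchanged. This rests on the planning SDs, simple unadjusted means, 300 subjects at Month 1 and a loss equal to the Study 201 LEM5 difference. The disagreement rates also rest on the assumed correlations. None of these is a forecast.

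The change should be made because it decides what may be concluded on a stated secondary objective. Primary and key secondary conclusions do not depend on it.

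The FAS model uses diary data collected after early drug stop. A reader might take this as a further fault, but protocol 9.7.1.6 chooses it openly ("When available, these data will be used for efficacy analyses"). An on-drug version would be a preference and is not part of this point.

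**What to change.** In SAP 3.4.2.4, for the Day-1 lemborexant arms:

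- Apply the protocol's rule separately at Months 3, 6, 9 and 12 against the Month 1 limit, and carry its definition of loss of effect into the SAP.
- Base the 12-month persistence conclusion on the Month 12 result.
- Label the Month 6 result '6-month persistence' and the former-placebo result 'persistence to about 6 months of exposure'.
- Record the change in SAP section 5.

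The rule should not require all four months to pass at once. The protocol flags each month separately, and a joint requirement would add chance failures. The wording should be settled before the sponsor is unblinded at the end of Period 1, so that the Month 12 rule is not chosen with results known.

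The cost is SAP wording; the monthly comparisons are already planned. The downside is that Month 12 rests on fewer subjects. With no true loss and 120 remaining, the Step 3 formula gives a chance crossing of the sWASO limit of 1 − Φ(4.87/s), about 9% to 12%, against 6% to 10% at Month 6 with 150 remaining. The number of subjects contributing should be shown beside each monthly result.

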9.7.1.1 Study Endpoints

The following endpoints will be analyzed for LEM5 and LEM10 compared to PBO.

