3 STATISTICAL METHODS

All statistical analyses will be performed by the sponsor or designee. When all subjects have completed Treatment Period 1 (Period 1), all data will be unblinded to the sponsor. There will be 3 database locks. The first will be of Period 1 data only, where data up to and including the visit at Month 6 will be analyzed. The second will include all data (Period 1 and ongoing Period 2 data) after all continuing subjects have completed the Month 9 (Period 2) visit, all available data will be analyzed to support regulatory submissions. The third will include all data where the study has continued to completion.

For the Period 1 analysis, sponsor staff and certain designees (detailed in the Study Integrity Charter) will be unblinded to the treatment allocation; however, subjects, investigators, and site personnel will remain blinded. These are not considered formal interim analyses since the primary and key secondary efficacy endpoints are all at Month 6 (Period 1), and there is no placebo control group in Period 2. Therefore, no Type I error adjustment is needed for efficacy analysis.

All descriptive statistics for continuous variables will be reported using number of observations (n), mean (arithmetic unless otherwise specified), standard deviation (SD), median, minimum and maximum. Categorical variables will be summarized as number and percentage of subjects. In summaries for safety the denominator for all percentages will be the number of subjects in a given treatment group. sSOL will be log transformed in analyses unless otherwise stated.

All statistical tests will be based on the 5% level of significance (two-sided).

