3.4.2.4 Other Secondary Efficacy Analyses

For all other secondary endpoints described below, the continuous variable will be summarized by using descriptive statistics by time point and the categorical variable will be summarized as the number and percentage of subjects by time point.

Unless is covered from the same model from the primary and secondary efficacy endpoints, or specified otherwise, the change from baseline assessments will be analyzed using MMRM assuming MAR (no missing value imputation) and the portion of responders will be analyzed using the Cochran Mantel Haenszel (CMH) test adjusted for region and age group. Missing values will be considered as non-responders in all responder analyses. No multiplicity adjustment will be made for all analyses.

The following endpoints will be analyzed.

EFFICACY MEASURES DERIVED FROM THE SLEEP DIARY

- Change from Study Baseline of mean sSOL, mean sSE, mean sWASO and mean sTST for the 1st 7 nights, Months 1, 2, 3, 4 and 5; and mean sTST at Month 6; for LEM5 and LEM10 compared to PBO
- Change from Study Baseline/ Treatment Period 2 Baseline of mean sSOL, mean sSE, mean sWASO and mean sTST for 1, 3, 6, 9 and 12 months exposure to LEM5 and LEM10. . Data from subjects randomized to LEM5 or LEM10 at the start of the study will use Study Baseline, data from subjects who were re-randomized to LEM5 or LEM10 in Period 2 will use Treatment Period 2 Baseline.
- The proportion of responders, separately for sSOL and sWASO, will be analyzed, for the first 7 nights, Months 1, 2, 3, 4, 5 and 6 for LEM5 and LEM10 compared to PBO:
 - The sleep onset responder is defined as: sSOL at Study Baseline is >30 minutes and mean sSOL at each month (first 7 nights, Months 1, 2, 3, 4, 5, 6) is ≤ 20 minutes,
 - The sleep maintenance responder is defined as: sWASO at Study Baseline is >60 minutes and mean sWASO at each month (first 7 nights, Months 1, 2, 3, 4, 5, 6) is ≤ 60 minutes and shows a reduction of >10 minutes compared to Study Baseline.

The proportion of responders will be analyzed based on the subjects with sSOL > 30 minutes at the baseline for sSOL and separately the subjects with sWASO > 60 minutes at the baseline for sWASO.

- The proportion of responders, separately for sSOL and sWASO, at Months 7, 8, 9, 10, 11 and 12 will also be summarized by using two types of baseline (ie., Study Baseline, Period 2 Baseline). The definition of the responder at Month 7, 8, 9, 10, 11 and 12 will be as follows:

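### The Month 1 to Month 6 persistence verdict has no placebo term, so it can be declared present although the drug-placebo difference has shrunk

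*SAP*

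**What the plan says.** The persistence paragraph of SAP Section 3.4.2.4 first says what the interval is for: "The 95% CI for the change from Study Baseline of sSOL, sSE, sWASO and sTST at each visit will be calculated using the MMRM" under MAR, with treatment, visit and treatment-by-visit in the model, on the FAS. It then gives the verdict. For sSE and sTST, "Persistence of effect will be defined as present if the mean change from Study Baseline at Month 6 is above the lower bound" of the Month 1 interval. For sSOL and sWASO, the Month 6 mean change must lie "below the upper bound of the 95% CI at Month 1 for sSOL and sWASO". No treatment difference is named. That the rule works on each arm's own change is therefore the natural reading, not the literal wording. The rebound text just before it does name a treatment difference.

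Protocol Section 9.7.1.6.2 defines the opposite state in the same way: "Loss of effect will be defined as present if the mean change from Study Baseline at Month 3", or a later month, falls outside the Month 1 interval on the unfavourable side.

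Placebo comparisons to Month 6 are planned, but separately. SAP Section 3.4.2.4 analyses the diary endpoints at the first 7 nights and at "Months 1, 2, 3, 4 and 5; and mean sTST at Month 6; for LEM5 and LEM10 compared to PBO". SAP Sections 3.4.1 and 3.4.2.1 test sSOL, sSE and sWASO against placebo at Month 6. After Month 6, SAP Section 3 notes that "there is no placebo control group in Period 2".

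**The concern.** An arm's change from baseline is the drug effect plus non-specific response. Protocol Section 9.2.2 expects large placebo effects in insomnia trials. If that response goes on improving between Month 1 and Month 6, it can offset a waning drug effect. The active arm's mean then barely moves, and the rule reports persistence.

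The rule also sets a later estimate against a limit of an earlier interval. That ignores the later estimate's own error and the correlation between visits. The allowance for worsening is the Month 1 half-width, so it grows as the sample shrinks.

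At stake is the answer to a stated secondary objective, persistence of efficacy over 12 months, for the half of the study in which a placebo reference exists.

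**Working it through.** **Inputs from the documents** (SAP Section 2; Protocol Section 9.7.2): sWASO SD of change 43 min, 300 per arm, design difference 11.4 min, two-sided 0.05. The sample-size text allows for discontinuation of up to 50% by Month 6, leaving 150 per arm. sWASO is used because it is analysed untransformed; sSOL is log-transformed, so minute-scale figures for it would only be illustrative.

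**Assumptions, not in the documents:** the Month 1 effect equals 11.4 min; the SD is 43 at both visits; the Month 1 to Month 6 correlation rho is 0.3, 0.5 or 0.7; placebo growth after Month 1 is as stated in each case.

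**The plan's own figure.** n = 2 × (1.96 + 1.2816)² × 43² / 11.4² = 299 per arm. The plan says 300, at which power is 90.1%. It reproduces. The documents give no error rate for the persistence rule.

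**Allowance built into the rule.**
- 300 per arm: 1.96 × 43/√300 = 4.87 min, and 4.87/11.4 = 43% of the design effect.
- 150 per arm: 1.96 × 43/√150 = 6.88 min, and 6.88/11.4 = 60%.

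**Probability that persistence is declared.** With d the net worsening of the active arm (drug effect lost minus placebo growth):

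P = Φ[(1.96 × SD/√n − d) / (SD × √(2(1 − rho)/n))]

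At 300 per arm the denominator is 2.94, 2.48 or 1.92 min for rho 0.3, 0.5 or 0.7.

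| Effect lost | Placebo growth | d | True LEM-PBO left | P at rho 0.3 / 0.5 / 0.7 |
|---|---|---|---|---|
| 11.4 | 11.4 | 0 | 0 | 95.1% / 97.5% / 99.4% |
| 11.4 | 8.55 | 2.85 | 0 | 75% / 79% / 85% |
| 11.4 | 0 | 11.4 | 0 | 1.3% / 0.4% / <0.1% |
| 5.7 | 5.7 | 0 | 5.7 | 95.1% / 97.5% / 99.4% |
| 5.7 | 0 | 5.7 | 5.7 | 39% / 37% / 33% |

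For a full loss, placebo growth alone produces the masking. For a half loss, the width of the allowance also contributes.

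**Placebo-referenced alternative.** The change in contrast, (LEM-PBO at Month 6) − (LEM-PBO at Month 1), has SE = √2 × the denominator above = 4.15, 3.51 or 2.72 min.
- Power to detect a full loss: 78%, 90% or 99%, whatever the placebo arm does.
- Power to detect a half loss (5.7 min): 28%, 37% or 55%.
- Applying the same CI-limit rule to the contrast (half-width 1.96 × 3.51 = 6.88 min) would still declare persistence after a half loss in 61%, 63% or 67% of trials. Carrying the pass/fail rule over to the contrast is therefore not a remedy.

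**The case against.** Much of the case on the other side stands.

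- A reader might infer that the report would hide a waning drug effect. The documents do not support that. LEM-PBO differences for sSOL, sSE, sWASO and sTST are planned at the first 7 nights and at Months 1 to 6, and responder rates against placebo over the same period. Shrinkage would be visible there.
- A reader might infer that regression to the mean inflates the verdict. Regression or placebo response already present at Month 1 enters both sides of the comparison and cancels. Diary baseline is also taken on placebo, over the last 7 mornings of the run-in (SAP Section 6.1.1). Only improvement after Month 1 can mask waning, and large placebo effects need not be growing ones.
- A reader might infer that small or noisy arms are favoured over others in Period 1. Allocation is about 1:1:1, and the sample code in SAP Section 7 fits one covariance matrix for all arms. Interval widths should be similar unless dropout differs. What remains is that the allowance widens for every arm as numbers fall.
- The within-arm form has a reason. The objective runs over 12 months, there is no placebo after Month 6, and this objective does not itself mention placebo. The lead-in to the endpoints in Protocol Section 9.7.1.1, "The following endpoints will be analyzed for LEM5 and LEM10 compared to PBO", also covers Period 2 endpoints, so it cannot by itself require a placebo-based rule.

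The objection does not answer one thing. No planned analysis estimates how far the placebo difference changed from Month 1 to Month 6, and the persistence verdict is not tied to the differences that are reported. A report could state that persistence is present beside contrasts that are shrinking.

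**Conclusion.** The concern holds for the Month 1 to Month 6 persistence label and no further. Where non-specific response improves after Month 1 by as much as the drug effect falls, the rule declares persistence with probability 95% to 99% for sWASO at 300 per arm, even if the whole 11.4 min effect is gone. Without such improvement a full loss is missed in at most 1.3% of trials. The result rests on assumed placebo growth, assumed correlations of 0.3 to 0.7, a Month 1 effect equal to the design difference, and equal SDs at the two visits.

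It would be too strong to conclude that the efficacy assessment is defective. Persistence is an additional secondary analysis without multiplicity control, and the gated primary and key secondary tests do not use it. This is a cheap improvement, not a threat to the trial's main conclusions.

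**What to change.** For Months 1 to 6, add to the MMRM already specified for persistence the contrast (LEM-PBO at Month 6) minus (LEM-PBO at Month 1), for each dose and endpoint. Give the estimate and 95% CI, on the log scale for sSOL, and base the Period 1 persistence statement on them. State in the SAP that an interval including zero is not proof of persistence, since power to detect a half loss in sWASO is only about 28% to 55%. Keep the within-arm description for Months 7 to 12, where no placebo group exists.

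Cost: 2 doses × 4 endpoints = 8 extra contrasts, with no new data or model. The interval is wider than for the within-arm change over the same visits, by a factor of √2 under the assumptions above.
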